Topical Antibiotics in Chronic Rhinosinusitis

NCT03673956

August 26, 2018

Topical Antibiotics in Chronic Rhinosinusitis

v3 8-26-18

i

PRÉCIS

Study Title

Topical Antibiotics in Chronic Rhinosinusitis

Objective

The primary objective is to show that the use of topical antibiotics in the treatment of chronic rhinosinusitis does not lead to antibiotic resistant organisms. The secondary objectives are to investigate the effects of topical antibiotics on patient symptoms as measured by the validated Sino-Nasal Outcomes Test (SNOT-22) and physical exam endoscopic findings as documented by Lund-Kennedy endoscopic scoring system.

Design and Outcomes

This is a prospective pilot study to evaluate development of antibiotic resistance in patients with chronic rhinosinusitis who are being treated with topical antibiotics.

Interventions and Duration

Intervention includes 28 days of culture directed antibiotic therapy with one of the following four topical antibiotics: Tobramycin, Mupirocin, Gentamicin or Levofloxacin

Sample Size and Population

There will be 20 participants total in the study and they will all receive the intervention.

STUDY TEAM ROSTER

Principal Investigator: [name]

[name], MD

[contact] [contact]

Co-Investigators:

[name] [contact]

[name] [contact]

Study Team:

[name] [contact]

[name], MS Biostatistician Phone:

[name], CCRP Research Coordinator

[name] Research Coordinator

Phone: Pager:

1 STUDY OBJECTIVES

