1.1 Primary Objective

The primary objective is to describe the results of antibiotic resistant organisms after the use of topical antibiotics in the treatment of chronic rhinosinusitis.

The secondary objectives are to investigate 1) the effects of topical antibiotics on patient symptoms as measured by the validated Sino-Nasal Outcomes Test (SNOT-22) and physical exam endoscopic findings as documented by Lund-Kennedy endoscopic scoring system. 2) the adherence to study intervention

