Our department has developed in conjunction with the infectious disease department and the Mayo pharmacy, an easy to implement set of topical antibiotics with easy to use capsules and set dosages for use by our patients. This is a pilot study designed with the hypothesis that topical antibiotics do not cause antibiotic resistance. In addition, data will be collected to investigate symptom and physical exam outcomes in patients undergoing topical antibiotic therapy as secondary outcomes. The study will be conducted on existing patients who would otherwise receive treatment with topical antibiotics as standard of care.

Moreover, many of patients who have recalcitrant chronic rhinosinusitis are infected by the bacteria pseudomonas aeruginosa. The use of the fluoroquinolone class of antibiotics is a treatment of choice for this pathogen. In 2008, the US Food and Drug Administration issued a "black box" advising manufacturers to warn providers and patients of risk increased risk of tendinitis, tendon rupture, peripheral neuropathy. A well-studied, viable alternative to oral fluoroquinolone that works well without the associated risks is warranted.

Finally, poor penetration of oral antibiotics to the sinonasal cavity due to the infection being within a space may limit the efficacy of oral antibiotics as a treatment. In contrast use of topical antibiotics in a patient who has previously undergone sinus surgery, provides a potentially more effective delivery of medication to the infected space⁸.

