3 STUDY DESIGN

This is a prospective, pilot study to investigate the presence or absence of antibiotic resistant organisms after treatment of chronic rhinosinusitis with topical antibiotics. In addition, therapeutic effects of the topical antibiotics will be investigated via assessment of patient symptoms, and physical exam endoscopic findings.

There will be 1 study group with 20 patients.

The patients will first undergo pre-intervention assessment in the outpatient setting. This will occur in the Department of Otorhinolaryngology on the 12th floor of the Gonda building in Rochester, MN with one of the staff rhinologists. Patients will be selected to participate if they have active mucopurulence on their endoscopic examination. The assessment will consist of 1) obtaining a nasal swab of mucopurulence from the affected sinus to be sent for gram stain, culture and sensitivity, 2) assessment of patient symptom severity score as measured by the self-administered Sino-Nasal Outcomes Test (SNOT-22) survey, and 3) assessment of patient physical exam as evaluated by rigid nasal endoscopy and documented in Lund-Kennedy endoscopic findings form.

The study intervention is the administration of culture directed topical antibiotics over 28 days. These antibiotics will prescribed to the patient in capsule form as compounded by the Mayo Clinic pharmacy, or suitable licensed compounding pharmacy. One capsule will subsequently be added to a nasal saline irrigation bottle, and the patient will administer this irrigation to him or herself in the usual fashion twice per day.

- The dosages of the antibiotic capsules were determined by the Mayo Clinic pharmacy team with input from infectious disease, based upon available published data, and will be as follows, dissolved in a standard 240mL saline irrigation rinse
 - Mupirocin: 30 mg
 - Tobramycin: 192 mg
 - Gentamicin: 192 mg
 - Levofloxacin: 250mg

After the completion of the study intervention (within 21 days), the patient will undergo post-intervention assessment in the outpatient setting, again in the Department of Otorhinolaryngology with one of the staff rhinologists. The patient will again be assessed with 1) nasal swab from the affected sinus sent for gram stain, culture and sensitivity 2) SNOT-22 symptom scores and 3) Lund-Kennedy endoscopic exam scores.

SELECTION AND ENROLLMENT OF PARTICIPANTS 4

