9 STATISTICAL CONSIDERATIONS

9.1 General Design Issues

This will be prospective single arm pilot study. We propose enrolling 40 patients in this study.

Measure of success is post-treatment assessment with nasal swab sent for gram stain, culture and sensitivity.

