9.2 Sample Size and Randomization

We propose enrolling 40 patients in this study. Since this study is a pilot study where we aim to describe the results and collect data for future larger study, sample size calculation is not required.

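### The précis sets out to show that topical antibiotics do not lead to resistance, but sections 1.1 and 9.2 aim only to describe, which is all this single-arm pilot can do

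*Combined protocol and SAP*

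**What the plan says.** Two statements claim an absence of effect. The précis gives the primary objective as "to show that the use of topical antibiotics in the treatment of chronic rhinosinusitis does not lead to antibiotic resistant organisms". Section 2.1 describes a pilot "designed with the hypothesis that topical antibiotics do not cause antibiotic resistance".

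Two other statements are descriptive. Section 1.1 reads "The primary objective is to describe the results of antibiotic resistant organisms after the use of topical antibiotics". Section 9.2 explains the lack of a sample size calculation by saying "we aim to describe the results and collect data for future larger study".

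The design is the same under either aim. Section 9.1 states "This will be prospective single arm pilot study". Sections 3 and 6.1 schedule a nasal swab with culture and sensitivities before treatment and another afterwards, which section 3 places within 21 days of completion. Section 5.1 allows a single 28-day course. Section 9.5 plans the number and proportion of patients who developed a resistant organism, with a 95% confidence interval. No section names a comparator, a test, a margin or a resistance rate that would count as acceptable.

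**The concern.** Both the précis and section 1.1 label their sentence as the primary objective, and the two call for different evidence. Showing that a treatment does not lead to an outcome is a causal claim of no effect. It needs something to stand for what would have happened without the drug, and a stated limit below which an excess is regarded as absent. The protocol has neither. It also relies on the descriptive aim to justify having no sample size calculation, while keeping the stronger claim as its headline.

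What is at stake is the conclusion the trial may draw. Section 2.1 says that perceived resistance risk limits wider use of these treatments, so the précis objective addresses a question that matters to practice. With the two objectives left side by side, a count of zero or a few could be read as meeting the précis objective. A few resistant isolates could equally be read as refuting the hypothesis when they reflect background turnover.

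**Working it through.** **Inputs.** Sample size is 20 in the précis and in section 3 ("There will be 1 study group with 20 patients"), and 40 in sections 9.1 and 9.2. The confidence level is 95% (section 9.5). The protocol gives no expected resistance rate, margin, alpha or power, so neither sample size can be reproduced. The true rates of 5% and 10% used below are assumptions. Section 9.5 names no interval method; the exact Clopper-Pearson interval is my choice.

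**Step 1: can the design attribute?** The baseline swab allows each patient's post-treatment culture to be compared with the culture before treatment. That is useful, because section 2.2 foresees pathogens already resistant at entry to tobramycin and gentamicin, or to mupirocin. The comparison describes emergence, but all patients are treated, so a change between swabs may reflect the drug, natural change in sinus flora, sampling variation between two swabs, or other exposures. On the last of these, section 4.2 excludes current or recent antibiotics at baseline, whereas section 5.3.3 lists only oral steroids as prohibited during the study. A resistant isolate after treatment therefore need not be due to the drug, and its absence does not show that the drug has no effect.

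**Step 2: how much would the best result exclude?** With 0 events in n patients, the two-sided 95% upper limit is 1 − 0.025^(1/n).

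- n = 20: 1 − 0.025^(1/20) = 16.8%
- n = 40: 1 − 0.025^(1/40) = 8.8%

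With one event the exact interval is 0.1% to 24.9% at n = 20 and 0.1% to 13.2% at n = 40.

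**Step 3: how often would zero events appear despite a real rate?** P(0 events) = (1 − p)^n.

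| Assumed true rate | n = 20 | n = 40 |
|---|---|---|
| 5% | 0.95^20 = 35.8% | 0.95^40 = 12.9% |
| 10% | 0.90^20 = 12.2% | 0.90^40 = 1.5% |

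At 40 patients, zero events would be fairly strong evidence against a rate of 10%, but not against 5%. At 20 patients it would be weak evidence against either. These figures concern only the rate of resistance in treated patients. Step 1 applies whatever the sample size.

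**The case against.** The best reply is that the sections governing conduct and analysis are already descriptive. Section 1.1 describes, section 3 looks at presence or absence, section 9.2 says the data serve a later, larger study, and section 9.5 plans an estimate with no test. Section 9.1 mentions a measure of success but attaches no threshold to it. The hypothesis in section 2.1 calls the study a pilot in the same sentence. On this view the précis is loosely worded and nothing in the design is at fault.

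Much of this stands. A single-arm descriptive pilot is legitimate, and the planned analysis is usable for that purpose. The reply does not remove the problem, because the claim in the précis is labelled the primary objective and is repeated as the study hypothesis.

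A reader might infer three stronger things that the documents do not support:

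- **That the trial needs a control arm, a margin or more patients.** That would follow only if the précis objective were kept. The declared aim in sections 1.1 and 9.2 requires none of them.
- **That a low count will be reported as proof of safety, or carried over to repeated courses.** Nothing in the protocol prescribes such a report. Section 5.1 limits the intervention to one course, and no section claims more.
- **That there is no baseline reference at all.** There is one, and section 9.5 counts patients who *developed* resistance.

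**Conclusion.** The concern holds as a conflict between stated objectives, one of which the design cannot meet. The précis objective and the section 2.1 hypothesis claim no causal effect, while sections 1.1 and 9.2 and the planned analysis support description only. The most favourable possible result would still be compatible with a resistance rate of up to 16.8% at 20 patients or 8.8% at 40. Those limits assume the exact interval and that all 20 or all 40 patients are evaluable; with fewer they would be higher. The zero-event probabilities rest on assumed true rates of 5% and 10%. The lack of attribution rests on no numerical assumption, since it follows from treating every patient.

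**What to change.** Reword the précis objective and the section 2.1 hypothesis to match the descriptive aim: to estimate, with a 95% confidence interval, the proportion of patients who developed a resistant organism relative to their baseline culture after one 28-day course. Keep the notion of *developed* from section 9.5. Section 9.4.1 speaks only of presence after treatment, and an objective worded that way would count resistance already there at entry.

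Add to section 9.5 that the result is read from the confidence interval, including its upper limit at the final number of evaluable patients, and that few or no events will not be taken as showing that treatment does not cause resistance.

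The limits calculated above should not be written into the plan. They belong to hypothetical results at two conflicting sample sizes, and the 20 versus 40 conflict has to be settled separately.

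The cost is a wording amendment, with no change to procedures, visits or sample size. The downside is a less favourable headline claim.

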1.1 Primary Objective

The primary objective is to describe the results of antibiotic resistant organisms after the use of topical antibiotics in the treatment of chronic rhinosinusitis.

The secondary objectives are to investigate 1) the effects of topical antibiotics on patient symptoms as measured by the validated Sino-Nasal Outcomes Test (SNOT-22) and physical exam endoscopic findings as documented by Lund-Kennedy endoscopic scoring system. 2) the adherence to study intervention

2 BACKGROUND AND RATIONALE

2.1 Background on Condition, Disease, or Other Primary Study Focus

There is a population of patients who have chronic rhinosinusitis that is refractory to maximal medical therapy including treatment with saline and steroid nasal irrigations as well as with oral steroids and antibiotics.

The evidence for use of topical antibiotics in current literature is conflicting. The few double blind randomized control studies cited have significant limitations including small sample size, variable intervention medications and delivery methods as well as variable outcomes measured¹⁻⁵. Other studies have shown that use of topical antibiotics in CRS has trended toward positive change in symptom score and endoscopic physical exam findings⁶. In addition, topical antibiotics are currently being used commonly at this institution for patients with recalcitrant chronic rhinosinusitis with good clinical anecdotal result. A well designed study is warranted to further investigate the utility of topical antibiotics in chronic rhinosinusitis.

One concern with topical antibiotics limiting widespread use is perceived increased risk of causing antibiotic resistance. Non-standardized dosage patterns has led to the concern that patients are potentially being treated with subtheraputic dosages. Others postulate that treatment with topical antibiotics against susceptible bacteria may have the effect of inducing biofilm production from resistant bacteria⁷. In contrast, advocates for topical antibiotics expect topical delivery to deliver high concentrations of antibiotics to the sinonasal cavity where they may penetrate a bacterial biofilm, and avoid the systemic effects of enteral or parenteral antibiotics⁷. Further study is warranted to further describe the potential association of topical antibiotic treatment of the sinonasal cavity with antibiotic resistance.

Our department has developed in conjunction with the infectious disease department and the Mayo pharmacy, an easy to implement set of topical antibiotics with easy to use capsules and set dosages for use by our patients. This is a pilot study designed with the hypothesis that topical antibiotics do not cause antibiotic resistance. In addition, data will be collected to investigate symptom and physical exam outcomes in patients undergoing topical antibiotic therapy as secondary outcomes. The study will be conducted on existing patients who would otherwise receive treatment with topical antibiotics as standard of care.

Moreover, many of patients who have recalcitrant chronic rhinosinusitis are infected by the bacteria pseudomonas aeruginosa. The use of the fluoroquinolone class of antibiotics is a treatment of choice for this pathogen. In 2008, the US Food and Drug Administration issued a "black box" advising manufacturers to warn providers and patients of risk increased risk of tendinitis, tendon rupture, peripheral neuropathy. A well-studied, viable alternative to oral fluoroquinolone that works well without the associated risks is warranted.

Finally, poor penetration of oral antibiotics to the sinonasal cavity due to the infection being within a space may limit the efficacy of oral antibiotics as a treatment. In contrast use of topical antibiotics in a patient who has previously undergone sinus surgery, provides a potentially more effective delivery of medication to the infected space⁸.

2.2 Study Rationale

The interventional regimen is as follows.

Patient will undergo pre-intervention nasal swab from the affected sinus that will be sent for gram stain and bacterial culture and sensitivities.

If pathogen identified in the bacterial culture is pseudomonas aeruginosa, topical tobramycin or gentamycin will be assigned as first line agent pending culture profiles and cost factors. If the sensitivities show resistance to both tobramycin and gentamycin, then levofloxacin will be prescribed.

If the pathogen identified in the bacterial culture is other than pseudomonas aeruginosa, mupirocin will be prescribed. If the pathogen shows resistance to mupirocin, then the patient will be prescribed one of the other three antibiotics will be prescribed pending culture profiles and cost factors

The patient will use the topical antibiotic twice a day for 28 days. This will be accomplished by first proceeding with their normal nasal rinse regimen as prescribed by their physician (this may include saline alone, or saline with budesonide). Twice per day, at the end of each regimen, they perform one additional nasal saline rinse using the Neil Med sinus rinse bottle in the manner outlined on the packaging instructions. However, with this last additional nasal saline rinse, they will open their antibiotic capsule and drop the contents into the rinse bottle prior to rinsing.

Known and potential risks are as follows:

Potential risks of nasal saline irrigation is stinging sensation and burning Potential risks of filling the nasal saline irrigation rinse bottle with water that is too hot is mucosal burns

Potential risks of topical antibiotic administration include local pruritis and inflammation Potential risks of selection antibiotic resistant organisms. Potential risk for hearing loss

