4.1 Inclusion Criteria

All participants in the study must meet all of the following inclusion criteria to participate in this study.

- Male or female, between 18-80 years old, diagnosed with chronic rhinosinusitis who have undergone previous functional endoscopic sinus surgery including at minimum maxillary antrostomy and anterior ethmoidectomy
- Active mucopurulence on endoscopic examination with corresponding culture demonstrating pathogenic bacterial growth
- · Completion of written informed consent
- No prior enrollment into this study
- Refractory to maximal medical therapy

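### The drug-assignment rule does not give every eligible culture a defined, culture-directed path, and the patients it misses blur the primary proportion

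*Combined protocol and SAP*

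**What the plan says.** **Intervention.** The Précis describes "28 days of culture directed antibiotic therapy with one of the following four topical antibiotics". Section 3 repeats the idea: "The study intervention is the administration of culture directed topical antibiotics over 28 days". Section 5.1 has the drug prescribed once the sensitivities are known, calls it the appropriate one without defining the word, and allows no modification.

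**Eligibility.** Section 4.1 requires "Active mucopurulence on endoscopic examination with corresponding culture demonstrating pathogenic bacterial growth". Nothing in 4.1 or 4.2 asks for susceptibility to a study drug, excludes an organism resistant to all of them, or limits entry to a single organism. The nearest exclusion in 4.2 concerns allergy.

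**Assignment rule, section 2.2.**
- P. aeruginosa: "topical tobramycin or gentamycin will be assigned as first line agent pending culture profiles and cost factors". The fallback is "If the sensitivities show resistance to both tobramycin and gentamycin, then levofloxacin will be prescribed".
- Any other pathogen: "If the pathogen identified in the bacterial culture is other than pseudomonas aeruginosa, mupirocin will be prescribed". If the pathogen is resistant to mupirocin, "one of the other three antibiotics will be prescribed pending culture profiles and cost factors".

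**Outcome.** Section 9.4.1 defines the primary outcome as a resistant organism being present after treatment. Section 9.5 counts the patients who developed one and gives a proportion with a 95% confidence interval.

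**The concern.** A trial of culture-directed therapy needs a rule that leads from each admissible culture to a treatment chosen on that culture. Here the entry criterion is wider than the rule. One fallback step is triggered by two other drugs' results and is silent on its own drug's result. Resistance to every permitted drug and mixed growth are not provided for.

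The statistical stake is the meaning of the primary proportion. The study asks whether topical therapy is followed by resistance. A patient whose organism was already resistant to the assigned drug at baseline cannot answer that. Under section 9.4.1 the patient can be a positive that therapy did not cause. Under section 9.5 the patient cannot become an event through that organism, yet still sits in the denominator. In mixed growth, the organism that did not decide the drug can persist and be reported as resistant after therapy in the same way.

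The gap is also hard to close informally. Section 10.3.3 restricts the data used to those in keeping with the protocol, so a clinician who departs from the literal step puts that patient's data at risk. Enrollment takes place at the screening visit (6.2.2), before the sensitivities are known (5.1), and section 4.3 keeps no record of ineligibility. An enrolled patient for whom no drug fits could drop out of the count without trace.

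**Working it through.** The plan gives no figure to reproduce: section 9.2 says no sample size calculation is required. The check is a reading of the rule case by case, followed by a calculation of scale.

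**Step 1. Each kind of eligible culture against section 2.2.**

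| Baseline culture | What the rule gives | Defined and matched to the culture? |
|---|---|---|
| P. aeruginosa, susceptible to tobramycin or gentamicin | One of these, with reference to the culture | Yes |
| P. aeruginosa, resistant to both, susceptible to levofloxacin | Levofloxacin | Yes |
| P. aeruginosa, resistant to all three | Levofloxacin, despite the reported result | No |
| Other pathogen, not resistant to mupirocin | Mupirocin | Yes |
| Other pathogen, resistant to mupirocin, susceptible to another listed drug | One of the other three, with reference to the culture | Yes |
| Other pathogen, resistant to all four | No matched drug and no stated path | No |
| P. aeruginosa plus another pathogen | Both branches apply; different first-line drugs; one drug allowed | Not defined |

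Three of the seven cases are open. All seven satisfy section 4.1 as far as the culture is concerned.

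**Step 2. Scale of one affected patient.** The Précis and section 3 give 20 patients; sections 9.1 and 9.2 give 40. Both are shown. Section 9.5 does not name an interval method, so the exact (Clopper-Pearson) interval is assumed. Its limits for x events in n are the 2.5% point of Beta(x, n−x+1) and the 97.5% point of Beta(x+1, n−x). For x = 0 the upper limit is 1 − 0.025^(1/n).

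| Events/n | Proportion | Exact 95% CI |
|---|---|---|
| 0/20 | 0% | 0 to 16.8% |
| 1/20 | 5.0% | 0.1 to 24.9% |
| 0/40 | 0% | 0 to 8.8% |
| 1/40 | 2.5% | 0.1 to 13.2% |

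This is the shift if the affected patient is counted as an event.

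**Step 3. The other reading.** If the patient is not an event but stays in the denominator, the effect is a false gain in precision. Taking one such patient out of 20 with no events gives an upper limit of 1 − 0.025^(1/19) = 17.6% instead of 16.8%. Taking one out of 40 gives 1 − 0.025^(1/39) = 9.0% instead of 8.8%.

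**Step 4. Chance that the problem arises at all.** The share q of enrolled patients in the three open cases is not in the documents. The chance of at least one is 1 − (1 − q)^n. The values of q are assumptions.

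| Assumed q | n = 20 | n = 40 |
|---|---|---|
| 1% | 18% | 33% |
| 5% | 64% | 87% |
| 10% | 88% | 98.5% |

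**The case against.** The strongest reply is that section 2.2 should be read with the Précis and sections 3 and 5.1. These make the intervention culture directed and the prescription the appropriate one after sensitivities, so no clinician would give levofloxacin against a resistant report. As a prediction of practice this is fair. It does not repair the text: section 2.2 is the only place that specifies the choice, and sections 5.1 and 10.3.3 discourage departures from it.

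A second reply is that the distortion comes only from the different wording of sections 9.4.1 and 9.5, which is a separate matter. It does not: a patient already resistant to the assigned drug is a false positive under one wording and not at risk under the other.

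A third is that this is a descriptive pilot and the number affected may be zero. That stands, and it limits the weight of the point.

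Four stronger readings are tempting, and the documents do not support them:
- A reader might infer that levofloxacin is always given without regard to its result. The silence is in the P. aeruginosa branch only; the other route to levofloxacin refers to the culture profile.
- A reader might infer that patients with mixed growth cannot receive culture-directed therapy. The rule is silent rather than prohibitive, and one listed drug might cover both organisms. The conflict appears only when both single-pathogen branches are applied together.
- A reader might apply a general mixed-growth rate to estimate how many patients fall under both branches. The documents give no rate, and two organisms that are both not P. aeruginosa fall under one branch only.
- A reader might infer that such patients receive an inactive drug. The documents do not say that a resistant laboratory result means no activity in a rinse, and section 2.1 notes that advocates expect high local concentrations.

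**Conclusion.** The point holds as a conflict between the entry criterion, the assignment rule and the stated intervention, with three specific gaps: a P. aeruginosa fallback that ignores the levofloxacin result, no path for resistance to every permitted drug, and no tie-break when P. aeruginosa grows with another pathogen.

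The total effect on the primary result cannot be sized from the documents. Per patient it is 5.0 points at n = 20 or 2.5 points at n = 40 if counted as an event, which assumes that the resistant organism is still found after treatment and is scored as positive. If the patient is merely left in the denominator, the effect is small: under one point on the upper limit at either size when there are no events.

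This should be corrected, because the wording conflicts with the trial's own definition of its treatment and the analytic remedy is cheap. It does not undermine the pilot as a whole.

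**What to change.** **Protocol.** Reconcile sections 2.2, 4.1, 4.2, 5.1 and 6.2.2 so that every culture that qualifies for entry has a defined path, including resistance to all permitted drugs and growth of P. aeruginosa with another pathogen. Which drug or clinical rule applies is for the study team. If the team settles this through eligibility, the order of events in 6.2.2 would have to change, because enrollment now precedes the sensitivity report.

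**Analysis (9.4.1 and 9.5).**
- Record for each baseline organism whether it was susceptible or resistant to the drug assigned. In mixed growth, classify each organism on its own result.
- Report the primary outcome by organism.
- Show separately the patients whose baseline organism was already resistant to the assigned drug. They should be neither counted as having developed resistance nor left in the at-risk denominator.
- Account for every enrolled patient who was not dosed, with the reason.

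**Cost.** The baseline sensitivities are already obtained before prescribing, so no new test is needed. The price is some extra tabulation and a somewhat smaller at-risk denominator, hence a slightly wider interval, as in step 3 of the working. Any change to the enrollment sequence would cost more than wording alone.
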